3.4. Informed Consent and Confirmation of Eligibility

Informed consent will be obtained through Qualtrics survey software from each participant prior to initiation of study tasks. Study personnel will obtain informed consent from participants and answer questions about the study or informed consent process prior to beginning study activities. Following informed consent, participants will complete a demographics questionnaire through Qualtrics that also includes items assessing history of suicide attempts from the Self-Injurious Thoughts and behaviors Interview (Nock, Holmberg, Photos, & Michel, 2007) for study eligibility determination and randomization purposes as well as the Suicide Visual Analog Scale (Bryan, 2019). Regardless of eligibility, all participants will be provided with contact information for crisis resources including the National Suicide Prevention Lifeline and Veterans Crisis Line.

3.5. Randomization to Study Conditions.

REDCap, a secure online survey and data management system maintained by The Ohio State University, will be utilized to randomize participants to study conditions immediately after obtaining demographic information (man, woman, other) and information about suicide attempt history (no suicide attempts, one suicide attempt, more than one suicide attempt) obtained from the SITBI). Participants will be randomized using stratified blocks of 6 or 8 participants, per recommendations by Krenan et al. (1999). After randomization, each participant will complete the remainder of the research study, but will be presented with one of the following pages containing instructions for completing the MMPI-2-RF-EX.

MMPI Condition 1 (Standard Instructions): “We want you to imagine that you are undergoing psychological testing as part of standard intake procedures for receiving services in a mental health clinic, which involves completing some questionnaires and a personality test before the first session. Please answer the questionnaires as honestly as you can, as your mental health care provider will use the results of your testing to develop your treatment plan. Please note, the questionnaire has some “lie” scales built into it that detect false responding. Additionally, as part of the intake process, you agreed to identify questions that you think are assessing your current risk of suicide. You will open the link to this portion of the study that was sent to you by study personnel to complete this.”

MMPI Condition 2 (Simulated Underreporting): “We want you to imagine that you are undergoing testing as part of standard intake procedures for receiving services in a mental health clinic, which involves completing some questionnaires and a personality test before the first session. You have recently had recurring thoughts of suicide and have thought of ways to attempt suicide. However, you are concerned that you will be hospitalized if you disclose this during testing and do not want to be hospitalized. Please answer the questionnaires as though you are trying to hide or downplay any thoughts of suicide or intent to make a suicide attempt. The questionnaire has some “lie” scales built into it, so try to avoid being detected. If you are able to avoid detection, you will receive an additional \$20 gift card. Additionally, as part of the intake process, you agreed to identify questions that you think are assessing your current risk of suicide. You will use a computer to mark these while taking the questionnaires.”

3.6. Additional incentives following completion of the first portion of the study.

Following the study session, all participants will receive payment in the form of \$50 for participation. Additional incentives are condition-dependent, will be described to participants at the beginning of the study as part of the informed consent process, and administered no later than two weeks following completion of the study protocol:

Simulated Underreporting: Additional payment for undetected underreporting on MMPI-2-RF-EX. Individuals in the Simulated Underreporting condition who do not produce clinically significant MMPI-2-RF-EX K or L scale elevations and are classified as Simulation Compliant based on Posttest Inquiry responses will receive an additional electronic \$20 gift card through email, following recommendations and procedures outlined in previous research (Brown & Sellbom, 2020; Crighton et al., 2017).

3.4. Detailed Study Procedures. One hundred and fifty adult military Veteran participants residing in the United States will complete eight study components during the baseline study session:

consenting, demographics survey and self-reported history of suicide attempts, randomization to study conditions, the MMPI-2-RF-EX, self-report measures, and the post-test survey to assess compliance with study instructions. Consenting procedures will always be completed first, and demographic and suicide attempt history data will always be collected second for randomization to conditions in both components of the study through REDCap online software. We estimate that the total participation time will be approximately 2.5 hours (2 hours to complete the MMPI-2-RF-EX and extra-test self-report measures. In order to protect participant confidentiality, password-protected Zoom or phone-based sessions will be conducted during the baseline session, in order to ensure security of MMPI-2-RF-EX items. All data will be collected through the Qualtrics, and non-PHI demographic information will be entered into REDCap system for randomization purposes. ID numbers will be linked to all data collected in the study, including identifying information collected in a separate data set as part of safety procedures (See Section 3.7), which will be deleted at the conclusion of the study. All deidentified data will be downloaded and deleted from Qualtrics servers at the conclusion of the study and stored on the password protected OneDrive server hosted by OSU indefinitely for the proposed analyses and secondary analysis. Additionally, in order to protect participant privacy during the study, all study personnel will conduct study procedures from a private location, using a secure Internet connection and instruct all participants to do the same, if possible, and outline the risks of loss of privacy or confidentiality if the participant is unable to do so.

3.7. Internal Validity. A number of measures will be implemented to mitigate threats to internal and external validity. Specifically, the randomization procedures employed in the proposed research study (See Section 4.1.2) were selected to account for the potential influences of gender and suicide attempt status on study findings.

3.8 Data Analysis.

3.8.1. MMPI-2-RF-EX scale scores and extra test measures. Following methods employed in prior simulation research designs (Sellbom & Bagby, 2008), mean differences in scores on MMPI-2-RF-EX L, K, and SUI scales, and extratest measures of suicide risk (BSS), suicide-related cognition intensity (SCS), and measures of other psychopathology (PCL-5, Short Grit Scale) will be compared between Standard and Simulated Underreporting groups through a one-way Multivariate Analysis of Variance (MANOVA). Additionally, two stepwise hierarchical regression analyses will be conducted in order to assess the incremental predictive utility of MMPI-2-RF-EX K and L scales in identifying individuals classified in the Simulated Underreporting condition, consistent with previous literature (Sellbom & Bagby, 2008). The first model will contain the K scale in the first step and the L scale in the second step. The analysis will be repeated with the K and L scales entered into the opposite step.

3.9. Safety Procedures. During enrollment in the study, all participants, regardless of agreement to participate in both portions of the study, will provide their contact information (home address, telephone number, email address) and a telephone number for an alternate person that study personnel may contact in case of imminent suicide risk. Home addresses may be used to contact the participant's local emergency services in case of imminent suicide risk. If a subject reports suicidal ideation, or a research staff member becomes aware that the subject is at imminent risk to harm himself/herself, the following questions will be asked to clarify the nature of risk (and to identify those at imminent risk requiring consideration for hospitalization): (1) Do you have a plan for killing yourself and do you intend to act on the plan?; (2) Do you have a desire to kill yourself that you believe you might act on?; (3) Have you already taken steps to act on your plan? If so, what steps have you taken? Both iterations of the CRP, which is a recommended and empirically-supported strategy for reducing suicide risk, will include contact information for professional resources and crisis services, the National Suicide Prevention Lifeline phone number, and other local behavioral health clinics and emergency departments. These procedures have been used successfully by our research team in dozens of studies with acutely suicidal individuals, to include multiple clinical trials. All participants will be provided with contact information to use in case of crisis (National Suicide Prevention Lifeline, emergency services).

3. Bibliography

Anestis, M. D., & Green, B. A. (2015). The impact of varying levels of confidentiality on disclosure of suicidal thoughts in a sample of United States National Guard personnel. *Journal of Clinical Psychology*, 71, 1023-1030.

Beck, A. T., & Steer, R. A. (1991). *Manual for the Beck scale for suicide ideation*. San Antonio, TX: Psychological Corporation.

Beck, A. T., Ward, C. H., Mendelson, M., Mock, J., & Erbaugh, J. (1961). An inventory for measuring depression. *Archives of General Psychiatry*, 12, 57-62.

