Participants could develop mild to moderate emotional discomfort or frustration associated with completing questionnaires or answering interview questions assessing thoughts about suicide. This potential risk is expected to be comparable to the discomfort experienced when talking with a friend or acquaintance about these same topics. If discomfort is experienced, it is not expected to be severe or to last for more than a few minutes. Participants' *confidentiality could be breached* if their identifiers are inadvertently released or accessed by a third party. This risk is expected to be low because the data are not stored or analyzed in ways that are likely to reveal a subject's identity. Breach of confidentiality could also occur if an external party or individual hacks into the Zoom interface during a participant's session. Safeguards will be implemented to mitigate this risk, including using password-protected Zoom sessions.

2.3. Benefits of the Proposed Research Results of this proposed research will have implications for future suicide risk assessment and suicide prevention efforts in Veterans through enhancing methods of identifying and responding to those at risk of suicide that would otherwise be missed by traditional methods of suicide risk assessment (i.e. false negatives).

Procedures

3.1. Research Design. A two-arm randomized controlled simulation design will be employed in this proposed research. For both components of the study, participants will be randomized using stratified blocks of 6 or 8 participants, per recommendations by Krenan et al. (1999), based on gender and suicide attempt history (no history of suicide attempts, history of one suicide attempt, or history of multiple suicide attempts).

3.2. Sample. A sample of 150 Veterans will be included in the study and randomized to study conditions (75 in the Simulation condition and 75 in the Standard condition). Results of a priori power analyses conducted using G*Power software (Faul et al., 2007) indicate that a total sample of 150 will result in a highly-powered study ($\beta = .98\text{--}.99$) to detect medium-sized effects in all regression-based analyses. Therefore, although we anticipate low attrition from this study, the proposed sample size is sufficiently powered for the proposed analyses. Additionally, this sample size accounts for a roughly 15% rate of Non-Content-Based Invalid Responding observed in other simulation-based MMPI research (Crighton et al., 2017).

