Online recruitment methods for the study are include web-based survey and research recruitment systems (e.g., SurveyMonkey), listservs and forums, and social media sites (e.g., Facebook, Twitter, Reddit). Additionally, we are requesting use of ResearchMatch (RM), which is an NIH sponsored national registry for research volunteers. ResearchMatch (RM) and OSU have had a fully executed agreement since August 2009. The IRB of record for ResearchMatch is Vanderbilt University. The Principal Investigator will be authorized to recruit study participants.

We will enroll any prospective Veteran meeting inclusion criteria (18 years of age or older, US military veteran, death or suicidal ideation/suicide attempt within the past month) in the proposed study. Exclusion criteria include: non-Veteran status, acute intoxication or active psychosis precluding

provision of informed consent, an inability to communicate and comprehend English, residence outside the United States, and lack of past-month death/suicide ideation or attempt. Participants recruited through web-based survey and research and recruitment systems will provide consent for study personnel to initiate contact through email or phone call, while those recruited through other online methods (e.g., listservs, forums) will be provided contact information for study personnel in order to inquire about the study or schedule participation.

3.3 Measurement/Instrumentation. The following self-report measures will be administered through Qualtrics online survey software during baseline procedures as part of the proposed research:

MMPI-2-RF-EX. The MMPI-2-RF-EX The MMPI-2-RF-EX was developed for research purposes in order to develop the MMPI-3 (Ben-Porath & Tellegen, 2020), which is comprised of a subset of MMPI-2-RF-EX items. While completing the MMPI-2-RF-EX, all participants will be monitored remotely by study personnel using a web camera and OSU CarmenZoom to ensure test integrity, as required by the study funding agency. While completing the MMPI-2-RF-EX, participants will simultaneously select the MMPI-2-RF-EX item numbers corresponding to those they believe are assessing current suicide risk through a separate internet browser or tab opened to a link in Qualtrics provided by study personnel.

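### The item-marking sentence differs between the two instruction pages and neither page fully matches Section 3.3, so the task may be delivered unevenly by arm

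*Combined protocol and SAP*

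**What the plan says.** The procedure is in Section 3.3, under MMPI-2-RF-EX. During the test, "participants will simultaneously select the MMPI-2-RF-EX item numbers corresponding to those they believe are assessing current suicide risk", and they do so "through a separate internet browser or tab opened to a link in Qualtrics provided by study personnel". No distinction is made by arm. The same paragraph states that "all participants will be monitored remotely by study personnel using a web camera", for the purpose of test integrity.

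The wording that participants read is in Section 3.5, which presents one of two pages after randomization. Both pages tell participants that they have agreed to pick out the questions they believe measure their present suicide risk. The closing sentence then differs:

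- On the Standard page (Condition 1): "You will open the link to this portion of the study that was sent to you by study personnel to complete this".
- On the Simulated page (Condition 2): "You will use a computer to mark these while taking the questionnaires".

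Section 3.2 allocates "75 in the Simulation condition and 75 in the Standard condition". Section 3.8.1 compares the arms by one-way MANOVA on L, K, SUI, BSS, SCS, PCL-5 and Short Grit Scale scores, and then uses K and L in hierarchical regressions to identify the simulators. Neither analysis uses the item-marking data or has a term for when marking was done.

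**The concern.** In a simulation design, the two pages should differ only in what defines the manipulation: here the scenario, the instruction to be honest or to conceal, and the incentive. Item marking is not part of that. Section 3.3 sets it as a common task for everyone, and the plan gives no reason for describing it differently by arm.

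A Standard participant who relies on the page alone could take the link as a separate exercise to be done after the test. A simulator is told to mark while answering, and could take the instruction to cover more than the MMPI-2-RF-EX. Looking for suicide items while answering may change how those items are answered. If that happened more in one arm, part of the arm difference would come from a second task and not from the instruction to underreport. Randomization balances participants at entry; it does not remove a difference that the arm's own page introduces afterwards.

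**Working it through.** No figure in the plan depends on this point, so there is none to reproduce. The check is a comparison of the three texts.

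| Feature of the marking task | Section 3.3, all participants | Section 3.5, Standard page | Section 3.5, Simulated page |
|---|---|---|---|
| Timing | Simultaneous with the MMPI-2-RF-EX | Not stated | Concurrent |
| Route | Separate browser or tab, Qualtrics link from study personnel | Link from study personnel | A computer; no link mentioned |
| Scope | MMPI-2-RF-EX item numbers | Not stated beyond a portion of the study | Questionnaires in general |

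**Step 1: agreement with Section 3.3.** The Standard page agrees on route and omits timing. The Simulated page agrees on timing, omits the link and is looser on scope. Neither page gives all three elements.

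**Step 2: alignment with arm.** Each page is shown to one arm only, so the wording difference coincides with allocation: 75 + 75 = 150.

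**Step 3: what would have to be true for bias.** Let q be the share of an arm that marks concurrently, and let δ be the effect of concurrent marking on a mean score, taken for simplicity as equal in both arms. Then:

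observed arm difference = instruction effect + (q_simulated − q_standard) × δ

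If Section 3.3 is followed, q = 1 in both arms and the last term is (1 − 1) × δ = 0. Bias needs both a realised difference in q and a nonzero δ. The documents give no realised q, and neither the size nor the sign of δ. No numerical estimate is therefore offered.

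**Step 4: would the plan detect a difference in q?**

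- The three Posttest Inquiry questions used to judge compliance (Section 3.3) concern the instructions received and the effort to look suicidal or not suicidal. None asks about marking.
- Monitoring is described as protecting test integrity. It is not described as checking that marking is concurrent.
- The analyses in Section 3.8.1 do not use the timing of marking.

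Uneven timing could therefore occur without being noticed.

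**The case against.** The strongest reply is that the procedure already fixes the timing. Section 3.3 requires simultaneous marking with no distinction by arm, and staff watch every participant during the test. A Standard participant who marked items afterwards would be departing from the protocol, and no such departure is planned or described. The link on the Standard page is naturally read as the one that Section 3.3 defines for use during the test. Both pages give the same cue to look for suicide items, so simulators are not alone in being asked to search. Section 3.5 introduces both pages as instructions for the MMPI-2-RF-EX, which weakens the idea that marking spreads to the SCS or BSS. Attention to suicide content is also largely built into the simulation scenario.

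Most of this stands. It disposes of the stronger reading that a reader might infer: that simulators do a different concurrent task and that the arm contrasts are therefore confounded or their false-positive rate inflated. The documents do not support that reading. It needs the arms to differ in practice on something that Section 3.3 makes equal, together with an effect whose size and direction appear nowhere.

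What the reply does not answer is that Section 3.3 states the intent, while the pages are the written instructions that participants receive, and those are unequal. The plan names no check that would show whether staff made up the difference.

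**Conclusion.** This is a minor point that holds as a wording inconsistency with a possible consequence. The two pages instruct a common task differently, each page matches Section 3.3 only in part, and the difference coincides with arm. The result is an avoidable risk of uneven delivery, of unknown size and direction. It is not a demonstrated confound.

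The conclusion rests on two assumptions: that the pages are shown as printed in Section 3.5, and that no uniform spoken instruction, absent from the documents, supplies the missing elements. If staff do give the same spoken instruction to everyone, the practical risk is smaller still, but the written pages should still agree. The sample size and the planned tests are unaffected.

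**What to change.** Replace the closing sentence on both pages in Section 3.5 with one identical sentence that matches Section 3.3. For example: Please open the link that study personnel sent you and, as you complete the MMPI-2-RF-EX, mark the numbers of the items on that test that you think ask about current suicide risk; do this for the MMPI-2-RF-EX only. The pages would then differ only in the scenario, the honesty or concealment instruction, and the incentive.

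The cost is one sentence per page and routine IRB approval of the text, with no added participant time.

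If sessions have already been run with the present pages, compare the timing of marking by arm where the survey software recorded it, and report any difference alongside the main results.

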Posttest Inquiry. All participants will be administered the MMPI-2-RF-EX Posttest Inquiry (PTI) that has been administered in previous MMPI simulation studies (Creighton et al., 2017), based on recommendations by Rogers (2008). The PTI assesses participants' compliance with condition-specific instructions for completing the MMPI and was adapted for the proposed research. Responses to three questions from this survey ("What instructions did you receive for completing the research study"; "I tried to answer the questions so I would look like I am not suicidal?"; "I tried to appear as suicidal as I could when I took the test") will be examined to assess compliance with instructions. Simulators answering "To fake not having thoughts of suicide" to the first question will be classified as Simulation- Compliant. Alternatively, Simulators answering at least "most of the time" to the second item and "not at all" to the third item will be classified as Simulation-Noncompliant and excluded from analyses. Veterans in the Standard Instructions condition who comply with instructions (e.g., do not produce profiles indicative of content-based invalid responding) are classified as Standard - Compliant while those who do not will be classified as Standard - Noncompliant and excluded from analyses.

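### As written, the bonus for undetected underreporting does not verify that any underreporting took place

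*Combined protocol and SAP*

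**What the plan says.** All references are to the combined protocol and SAP.

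- **Section 3.6 (additional incentives).** The bonus is headed "Additional payment for undetected underreporting on MMPI-2-RF-EX". It goes to simulators "who do not produce clinically significant MMPI-2-RF-EX K or L scale elevations and are classified as Simulation Compliant", the second condition being judged from the Posttest Inquiry (PTI). The section says the incentives are described at consent and attributes the arrangement to earlier simulation studies.
- **Section 3.5, Condition 2.** Simulators are told: "Please answer the questionnaires as though you are trying to hide or downplay any thoughts of suicide or intent to make a suicide attempt". They are then warned about lie scales and told: "If you are able to avoid detection, you will receive an additional" gift card.
- **Section 3.3, Posttest Inquiry.** Three answers are examined. Item 1 asks which instructions were received. Item 2 asks whether the participant tried to look non-suicidal. Item 3 asks whether the participant tried to look suicidal. The rules are: "Simulators answering 'To fake not having thoughts of suicide' to the first question will be classified as Simulation- Compliant" and, presented as an alternative, "Simulators answering at least 'most of the time' to the second item and 'not at all' to the third item will be classified as Simulation-Noncompliant", with exclusion from the analyses.
- **Section 1.** H1 expects higher L and K in simulators. H2 expects lower SUI, SCS and BSS. H3 expects L and K each to add to the other in separating the groups.

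**The concern.** The name of the bonus has two halves, underreporting and going undetected, and the payment rule tests only the second. Evasion is scored through K and L. Concealment is not scored at all, and the label that might stand in for it rests on recall of an instruction rather than on conduct.

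A simulator who disregards the task and answers truthfully resembles a Standard participant. Each one retained in the simulation arm moves that arm's L and K down towards the Standard mean (H1), moves SUI, SCS and BSS up towards it (H2), and weakens the group label that the regressions try to predict (H3). Section 3.8.1 plans no sensitivity analysis that would reveal this.

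**Working it through.** **Step 1. Apply the rule to two simulators.** Both recall the instruction, and neither has a K or L elevation. A concealed suicidal thoughts and reports this in the PTI (item 2 at least *most of the time*, item 3 *not at all*). B answered honestly and reports not having tried to look non-suicidal. The outcome depends on how the two PTI sentences in Section 3.3 fit together.

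| Reading of Section 3.3 | A (concealed) | B (honest) |
|---|---|---|
| Item 1 alone decides | Compliant, paid, analysed | Compliant, paid, analysed |
| Items 2/3 as written, overriding item 1 | Noncompliant, unpaid, excluded | Compliant, paid, analysed |
| Items 2/3 mislabelled; an alternative route to Compliant | Compliant, paid, analysed | Compliant through item 1, paid, analysed |
| Items 2/3 mislabelled; required as well as item 1 | Compliant, paid, analysed | Noncompliant, unpaid, excluded |

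The first two rows follow from the text as it stands, and B is paid and analysed in both. Only the last row closes the gap, and the text does not state it.

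**Step 2. The plan's own power figure.** Section 3.2 gives .98 to .99 (printed as beta) for medium effects in the regression analyses with N = 150. The value of the medium effect and alpha are not stated; I assume f² = 0.15 and alpha = 0.05. With noncentrality λ = f²N = 0.15 × 150 = 22.5, the noncentral F test gives 0.997, 0.992 and 0.985 for one, two and three tested predictors. Section 3.2 also mentions about 15% invalid responding: 150 × 0.85 = 127.5, about 128, which gives 0.992 (one) and 0.979 (two). The stated figure reproduces to within 2 percentage points. It covers the regressions only, not the mean comparisons behind H1 and H2.

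**Step 3. What honest simulators would cost.** Let a share h of the simulators retained in the analysis answer like the Standard arm, with within-group SD 1 and true difference d. Then:

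- mean difference = d(1 − h)
- simulator variance = 1 + h(1 − h)d²
- effective d = d(1 − h) / √{[1 + 1 + h(1 − h)d²] / 2}

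For d = 0.5 and h = 0.2: 0.40 / √[(2 + 0.04) / 2] = 0.40 / 1.010 = 0.396.

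Power is for a two-sided 5% two-sample t test, with 75 per arm (Section 3.2) or 64 per arm (128 / 2).

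| h | Effective d (d = 0.5) | Power, 75 per arm | Power, 64 per arm | Effective d (d = 0.8) | Power, 75 per arm |
|---|---|---|---|---|---|
| 0 | 0.500 | 0.86 | 0.80 | 0.800 | 0.998 |
| 10% | 0.447 | 0.78 | 0.71 | 0.710 | 0.99 |
| 20% | 0.396 | 0.67 | 0.60 | 0.624 | 0.97 |
| 30% | 0.345 | 0.56 | 0.49 | 0.542 | 0.91 |

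Both d and h are assumptions; the documents give neither. The table describes one outcome tested alone, whereas Section 3.8.1 specifies a MANOVA and hierarchical regressions. It shows the cost of honest responding from any cause, not the part that the bonus induces.

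**The case against.** **The PTI does ask about conduct.** Section 3.3 says that all three answers are examined to assess compliance, and item 2 is about behaviour. If items 2 and 3 were meant as additional requirements, a simulator who answered honestly and said so would be unpaid and excluded. This stands as a limit: the loophole depends on wording that must be reconciled anyway. It does not remove the point, because the sentence as printed attaches the wrong label to reported concealment and item 1 alone confers compliance.

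**Condition 2 instructs concealment.** A reader might infer that participants are told payment depends on the lie scales alone. The page does not say so. It asks them to hide suicidal thoughts, then to avoid detection, then offers the money, and detection can naturally be read as detection of the hiding. What stands is narrower: the payment sentence itself names only evasion.

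**The bonus does not oppose H2.** A reader might infer that it does. Low SUI, SCS or BSS is never penalised, and concealing without elevating K or L earns the same money. H2 suffers only if some simulators ignore the instruction. Nor do the documents show that honesty is the surest way to be paid: they give no K or L cut-off, and Section 3.3 allows for Standard participants with content-based invalid profiles.

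**Rewarding evasion is deliberate.** Section 3.6 attributes it to earlier simulation studies. It makes H1 harder to show, not invalid, and excluding Standard participants with content-based invalid profiles pushes H1 the other way. This objection stands in full; the point concerns the missing underreporting half of the rule, not the reward for evasion.

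**Conclusion.** The point holds in a limited form. On the current wording of Sections 3.3 and 3.6, the bonus does not verify underreporting, and a simulator who answers honestly can be paid and analysed. That may dilute H1, H2 and H3.

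The extent is unknown. Under an assumed d of 0.5 and 75 per arm, 10% or 20% honest simulators would lower power for a single mean comparison from 0.86 to 0.78 or 0.67. At d = 0.8 the effect at 20% is minor. These figures assume that honest simulators score exactly as the Standard arm does on average.

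A reader might go further and conclude that the incentive makes a null result uninterpretable. The documents do not support that: they give no rate of honest responding, the instruction asks for concealment, and concealment that goes undetected is paid. It is an inexpensive inconsistency worth removing, not a fatal flaw.

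**What to change.** 1. **Condition 2 (Section 3.5) and consent text.** Reword the payment sentence so that it depends on both parts, for example: *If you hide thoughts of suicide and also avoid being detected, you will receive the additional gift card.*
2. **Posttest Inquiry (Section 3.3).** Reconcile the two classification sentences. Require for Simulation-Compliant status the correct answer to item 1 and also reported concealment: item 2 at least *most of the time* and item 3 *not at all*. Simulators who do not meet all three are Noncompliant.
3. **Bonus (Section 3.6).** Keep the K and L condition and refer to the revised Compliant status.

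Do not add a SUI threshold to the payment rule. It would pay one arm for an H2 outcome, so a positive SUI result could reflect the payment. It would also not prove concealment: Section 3.2 admits veterans with past-month death ideation alone, so a truthful simulator could still score low.

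The cost is an IRB wording amendment and slightly fewer bonuses. No new data are needed, since all three PTI items are already collected. The check still rests on self-report, so a simulator who answered honestly but claims to have concealed would not be caught.
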